**Hematologic DLT:**

- Grade 4 (NCI-CTCAE V5) neutropenia lasting > 3 days,
- Febrile neutropenia Grade 3 (ANC < 1,000/mm^3 with fever ≥ 38.5 °C) (CTCAE V5),
- Febrile neutropenia Grade 4 (life-threatening consequences; urgent intervention indicated),
- Grade 4 (NCI-CTCAE V5) anemia (i.e life-threatening consequences; urgent intervention indicated),
- Platelets < 25 000 /mm^3 or platelets < 50 000 /mm^3 associated with bleeding,
- INR or PTT elevation of Grade ≥ 3 (NCI-CTCAE V5) with associated bleeding,
- Grade ≥ 3 hemorrhage/bleeding events (NCI-CTCAE V5).

**Phase II:** 48-week disease-control rate (defined as the rate of non-progressing patients after central review, at 48-week post-initiation of therapy, to all treated patients.

Treated patients who have progressed or died before the 48-week evaluation will be considered as failure.

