**Prophylactic G-CSF will be systematically given after each course from Day-7 to Day 12.**

**REGORAFENIB** will be given orally at a dose of 80 to 160 mg, as per dose-level, once daily on days 4 to 10 of each cycle

Tumor assessments (computed tomography (CT) or magnetic resonance imaging (MRI)) of the chest, abdomen, pelvis (if patient allergic to iodine contrast agents) will be performed at the baseline, every 8 weeks thereafter.

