### **Phase II :**

The 6 patients treated at the RP2D in the phase I part will be included in the phase II part. The multicenter, phase II trial is planned to enroll 69 patients. The patients who meet the study eligibility criteria will be included to receive the study drug.

- ❖ **First inclusion:** april 2019
- ❖ **Inclusion period:** 12 months Phase I + 12 months Phase II
- ❖ **End of the inclusion period:** march 2021
- ❖ **Expected end of study:** june 2022
- ❖ **Report:** september-december 2022
- ❖ **Poster/public:** phase I (2020), phase II (april 2023 and july 2023)

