## 7. Blinded independent central review (BICR)

A central review of CT-scans is planned for patients found progression-free at 48 weeks. They will be submitted to a independent panel of radiologists for review of tumor response.

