#### Phase II

With a one-stage Fleming design,  $\alpha = 5\%$ ,  $\beta = 20\%$ ,  $p_0$  (the probability of inefficiency maximum) = 35% and  $p_1$  (the probability of minimum efficiency) = 50%, it would be necessary to include 65 evaluable patients (69 patients/ 5% non-evaluable patients).

The association can be considered sufficiently effective (reject null hypothesis) if there are at least 29 success (48 weeks disease control rate) out of 65 evaluable patients, the success rate is significantly greater than 35%.

The association can be considered insufficiently effective (reject alternative hypothesis) if there are 28 or less success out of 65 evaluable patients, the success rate is significantly lower than 50%.

In total, a maximum of 87 (=18 patients for phase I + 69 patients for phase II including 6 patients treated at the RP2D during the phase I) patients will be included.

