### 10.2. STUDY POPULATIONS

Different population of patients may be defined for the analysis:

- Intent To Treat (ITT) population: all included patients.
- Per-Protocol (PP) population: all eligible patients (patients with no major violations of the inclusion/exclusion criteria) and evaluable patients (included treated patients with evaluation at 48 weeks or without evaluation at 48 weeks if progressive or dead patient).
- Safety population: all treated patients who received at least one dose of treatment.

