### 10.3. STATISTICAL METHODS

A statistical analysis plan (PAS) will be written before the closed database. All statistical analyses will be performed on ITT population, on PP population for efficacy analysis and on Safety population for safety analysis. Populations are defined in section 10.2.

Descriptive analyses will be performed using median and range for continuous parameters, frequency and percentage for categorical variables.

Incidence rate of DLT and Incidence rates of adverse events and serious adverse events will be carried using frequencies and percentages at each dose level for phase 1.

The primary phase II endpoints 48 weeks disease control rates, will be described using percentage and its associated 95% confidence interval.

The median follow-up will be calculated using the reverse Kaplan-Meier method with its confidence interval of 95%.

All event free survival (PFS, OS) will be estimated using the Kaplan-Meier method, and then described using medians and rates with their associated 95% confidence interval.

Statistical analyses will be performed with STATA software (Stata Corporation, College Station, TX, USA).

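### The phase II primary endpoint is a rate over all treated patients, but the go/no-go rule counts 65 evaluable patients, a set whose membership depends on outcome, and no cut-off is given for the all-treated rate

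*Combined protocol and SAP*

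**What the plan says.** **Endpoint.** Section 2.2.1 (and the synopsis, study endpoints) defines 48-week disease control as a rate, "defined as the rate of non-progressing patients after central review, at 48-week post-initiation of therapy, to all treated patients". Section 2.2.1 adds: "Treated patients who have progressed or died before the 48-week evaluation will be considered as failure". It has no explicit rule for a treated patient whose week-48 status is unknown.

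**Decision rule.** Section 10.1 (and the synopsis, statistical considerations) calls the combination sufficiently effective "if there are at least 29 success (48 weeks disease control rate) out of 65 evaluable patients", and insufficiently effective at 28 or fewer. On numbers, section 3.1 says the "phase II trial is planned to enroll 69 patients", and section 10.1 explains the 69 as 65 plus a 5% allowance for non-evaluable patients.

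**Analysis sets.** Section 10.2 describes "evaluable patients (included treated patients with evaluation at 48 weeks or without evaluation at 48 weeks if progressive or dead patient"; the per-protocol (PP) set also requires no major eligibility violation. Section 10.3 states: "All statistical analyses will be performed on ITT population, on PP population for efficacy analysis and on Safety population for safety analysis". ITT is all included patients. The all-treated set, which is the endpoint's own denominator, is named only for safety.

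**Tumour status over time.** Section 7 says: "A central review of CT-scans is planned for patients found progression-free at 48 weeks". The synopsis says that imaging "will be performed at the baseline, every 8 weeks thereafter", and footnote 11 of the section 5.1 table repeats the 8-week interval. Section 9.4 runs response assessment to progression, but under objective response. Section 9.1 requires data collection to continue after treatment is discontinued, without naming imaging. The visit table and sections 5.4 and 5.5 list a conditional scan at end of treatment, a conditional scan at the 30-day visit, and none in the three-monthly follow-up.

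**The concern.** Two texts give different rates from the same data. A treated patient with no week-48 evaluation and no known progression or death cannot be found non-progressing after central review at week 48. Under section 2.2.1 that patient stays in the denominator and is not a success. Under section 10.2 the patient leaves the evaluable set. A patient who progressed or died always counts, while a patient who did not counts only if evaluated at week 48. Entry to the deciding set therefore depends on outcome.

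The single claim of an uncontrolled trial rests on this one proportion. If some treated patients lack week-48 status, the plan does not say whether the 65-patient rule, the all-treated rate or the ITT rate settles the matter, and it gives a cut-off only for the first. Section 10.3 requires a statistical analysis plan before database closure. In an open-label single-arm trial, week-48 outcomes may already be known by then.

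**Working it through.** **1. Reproducing the plan's figures.** Inputs from section 10.1: alpha 5% (one-sided, since only that gives 65), beta 20%, p0 = 0.35, p1 = 0.50.

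- n = [(1.645·√(0.35·0.65) + 0.842·√(0.50·0.50)) / 0.15]² = 64.57, so 65.
- 65/0.95 = 68.4, so 69.
- Cut-off: 65·0.35 + 1.645·√(65·0.35·0.65) = 29.08, printed as 29.

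The design reproduces. By exact binomial, at least 29/65 has alpha 0.069 and power 0.839; at least 30/65 has 0.041 and 0.771. That the printed cut-off exceeds 5% is a separate problem.

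**2. Effect of the denominator.** Let m be the number of treated patients without week-48 status who are not known to have progressed or died, with 65 evaluable, so that n treated = 65 + m. The plan's allowance is 4 non-evaluable patients of any kind, some of whom may never be treated, so m = 0 to 4 is an illustration. Exact one-sided p = P(X ≥ k | n, 0.35):

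| Successes k | n = 65 | 66 | 67 | 68 | 69 |
|---|---|---|---|---|---|
| 29 | 0.069 | 0.083 | 0.099 | 0.117 | 0.137 |
| 30 | 0.041 | 0.051 | 0.062 | 0.075 | 0.090 |
| 31 | 0.024 | 0.030 | 0.037 | 0.046 | 0.056 |

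Twenty-nine successes are 29/65 = 44.6% or 29/69 = 42.0%. With 30 successes, a test at the stated 5% changes its answer from m = 1 (only just at m = 1). With 31 it changes only at m = 4.

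**3. Direction of error.** Take a true 48-week control rate of 35% and a cut-off of 30/65, used here to keep the printed cut-off's own excess out of the comparison. Let u = m/(65 + m).

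- *Losses independent of progression* (assumed constant competing hazards over 48 weeks). Progression hazard h = −ln 0.35 = 1.050; loss hazard c solves c/(c+h)·(1 − e^−(c+h)) = u; evaluable rate = e^−(c+h)/(1 − u). For m = 4: u = 0.0580, c = 0.0974, rate = 0.3175/0.9420 = 0.337. False-positive rates for m = 1 to 4: 0.037, 0.032, 0.028, 0.025.
- *All lost patients would have progressed.* Rate = 0.35/(1 − u). False-positive rates: 0.050, 0.061, 0.073, 0.086.
- *Three of four would have progressed* (m = 4). Rate = (0.35 − 0.25u)/(1 − u) = 0.356. False-positive rate 0.052.
- *All lost patients would have been controlled.* Rate = (0.35 − u)/(1 − u). False-positive rates: 0.028, 0.019, 0.012, 0.007.

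**4. Cut-offs on all treated patients.** The smallest k with exact alpha at or below 5% is 31 at n = 68 (alpha 0.046, power 0.802) and 32 at n = 69 (alpha 0.034, power 0.765).

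**5. Power when missing counts as non-success.** True rate 50%, losses independent as in step 3 with h = −ln 0.50. With 2 of 69 unassessed the all-treated success rate is 0.480, and at least 32/69 has power 0.65. With 4 of 69 it is 0.460, and power is 0.52.

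**The case against.** Inflating 65 to 69 for non-evaluable patients is a common planning device, and the printed rule can be run as written if exactly 65 are evaluable. Section 2.2.1, read literally, already makes unassessed patients non-successes; section 10.3 has both ITT and PP reported; and an analysis plan is to follow. An evaluable-set primary analysis with a missing-as-failure sensitivity analysis is also defensible. All of this stands as far as it goes. It does not remove the mismatch between the defined endpoint and the deciding count, or supply a cut-off for the former.

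A reader might infer that dropping unassessed non-progressors inflates the false-positive rate in general. The calculations do not support that: if losses are independent of progression the rate falls below 5%, and it rises above 5% only when most or all of the lost would have progressed. The changes of conclusion at 30 and 31 successes also arise from a 5% exact test, not from the printed count of 29.

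A reader might also infer that the protocol stops scans when treatment stops. No passage says so. The visit lists are silent while other passages suggest continued follow-up, and the passage running to progression concerns objective response. This is a point to clarify, and the documents give no number of patients affected.

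Finally, the evaluable definition drops only unassessed non-progressors *among treated patients*. If the 65 are meant to be the full PP set, major eligibility violators are dropped too; section 10.1 does not say which.

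**Conclusion.** The point holds as an inconsistency in the primary analysis. The endpoint's denominator is all treated patients, the decision's is evaluable patients, and the two differ by a group selected on outcome. At the planned allowance, if all 4 non-evaluable patients were treated, the gap at 29 successes is 2.6 percentage points (44.6% against 42.0%). A single unassessed treated patient can move a result of 30 successes across 5%. The direction of error cannot be fixed in advance: with four lost and a 30/65 cut-off, the false-positive rate runs from 0.007 if all would have been controlled, through 0.025 under independent loss, to 0.052 if three of four and 0.086 if all four would have progressed. These figures rest on m = 0 to 4 and on the constant-hazard model for independent losses; neither is a protocol figure. The case rests on an ambiguous deciding rate, not on a demonstrated inflation of error.

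**What to change.** In sections 10.1 to 10.3, and the matching synopsis text:

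- Name all treated phase II patients, including those treated at the RP2D in phase I, as the primary decision set, in line with section 2.2.1.
- State that a missing week-48 status counts as non-success.
- Give the exact cut-off for the actual treated n with its true alpha and power (at least 31/68: 0.046 and 0.802; at least 32/69: 0.034 and 0.765), and restate the design's power accordingly.
- Report the evaluable/PP rate, a bound with missing counted as success, and the Kaplan-Meier 48-week rate as sensitivity analyses.

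As a supporting clarification, reconcile sections 5.1, 5.4, 5.5 and 7.1 with the synopsis imaging statement, footnote 11 and sections 9.1 and 9.4. Tumour status at week 48, with a stated window, should be recorded and sent for central review for patients who stop treatment without progression. State also how patients who start another anti-cancer therapy before week 48 are counted.

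**Cost.** Mostly wording, plus collecting week-48 status off treatment. The statistical price is power: at 32/69 and a true rate of 50%, it falls from 0.765 to about 0.65 with 2 unassessed and 0.52 with 4, under independent losses. Collecting week-48 status is the practical protection, though it cannot recover patients who withdraw consent or are lost to follow-up. No increase in sample size is proposed. All of this should be fixed before week-48 outcomes are known.

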### 2.2.2 Secondary endpoints

- Progression-free survival (PFS), defined as the time from date of inclusion to date of first observed disease progression (investigator's radiological or clinical assessment) or death due to any cause, if death occurs before progression is documented. A central review of CT-scans is planned for patients found progression-free at 48 weeks. Patients without tumor progression or death at the time of analysis will be censored at their last date of tumor assessment.
- Disease control rate (DCR), defined as the rate of patients with non-progressive disease (i.e., CR, PR or SD), to all includes patients.

- Objective response rate (ORR), defined as the rate of patients with CR or PR, to all patients included.
- Deepness of response (DpR) is defined as the relative change in the sum of longest diameters of RECIST target lesions at the nadir, in the absence of new lesions or progression of non-target lesions, as compared to baseline.
- Time to recurrence under maintenance, defined as the time (days) from date of chemotherapy discontinuation (for protocol reasons) and regorafenib continuation (as maintenance treatment) to date of first observed disease progression (investigator's radiological or clinical assessment) or death due to any cause, if death occurs before progression is documented. Patients without tumor progression or death at the time of analysis will be censored at their last date of tumor assessment.
- Overall survival (OS), defined as the time (months) from date of inclusion to date of death. Patients lost for follow-up at the time of analysis will be censored at their last news.
- Resection (R) rates: R relates to resection margins. R0/R1 are classified by the pathologist and R2 is classified by the surgeon. R0 is defined as the absence of cancer cells seen microscopically at the resection margin. R1 is defined as the presence of cancer cells microscopically at the resection margin (microscopic positive margin). R2 is defined at gross examination with the presence of tumor tissue at the resection margin.

Resectability rate (R0R1) and unresectability rate (including R2) among patients with liver-only metastases.

As translational studies:

- Central determination of cfDNA levels at baseline, every 8 weeks during treatment and at the end of treatment.
- Impact of DDR1 kinase activity on response and PFS, and study of the variation of DDR1 activity in patients whom liver metastases are deemed resectable.

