## 1. Background and rationale

### Colorectal cancer

Colorectal cancer (CRC) is a major cause of morbidity and mortality globally. More than 50% of patients can be expected to develop metastatic disease, and most of these patients will require palliative systemic therapy. The primary goal for patients who present with technically resectable liver metastases is definitely cure, with R0 resection as the primary goal. However, any patient with limited liver and/or lung metastases should be considered a candidate for potential secondary resection as there are no criteria that allow physicians to distinguish between those patients for whom purely palliative treatment and those for whom potentially curative treatment is appropriate. Although survival times are slightly shorter for patients who undergo conversion therapy followed by surgery than for patients with initially resectable metastatic disease, they are far better than if resection is not carried out at all (1).

As per ESMO guidelines, first-line therapy commonly involves the doublet (2-CT) regimens of 5-fluorouracil, folinic acid, and either oxaliplatin (FOLFOX) or irinotecan (FOLFIRI). The addition of targeted therapies, such as bevacizumab (a pure anti-angiogenic agent which binds circulating VEGF-A), cetuximab, and panitumumab, to FOLFOX or FOLFIRI may be helpful to some patients in improving tumor response and ultimately overall survival. The cytotoxic triplet (3-CT) FOLFOXIRI with or without bevacizumab may be an option in selected fit and motivated patients when cytoreduction (tumour shrinkage) is needed to undergo conversion therapy (1).

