## 6.4 Treatment duration

12 cycles have to be delivered consecutively or not.

Indeed, treatment can be temporarily stopped to perform surgical resection or regional procedures (radiofrequency, cryoablation, radiation therapy) if the disease become accessible to them but if it happens, before the end of the 12 planned cycles, the treatment

has to be resumed within 4 to 8 weeks after the loco-regional procedure has been completed in order to reach a total number of 12 cycles delivered.

If a surgery or a regional procedure is considered, we recommend respecting a time period of 4 weeks between the last chemotherapy and the procedure.

After 12 cycles, patients whose metastases are not progressing and are still unresectable will receive regorafenib (experimental regimen and at the same dose) until progression or toxicity.

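### R0, R1 and R2 are defined only at the resection margin, so a clear-margin partial resection that leaves gross liver metastases behind counts as resectable, while clearance by ablation alone cannot be scored

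*Combined protocol and SAP*

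**What the plan says.** Section 2.2.2 opens the definition with "R relates to resection margins". It then states that "R0 is defined as the absence of cancer cells seen microscopically at the resection margin", that R1 is a microscopically positive margin, and that "R2 is defined at gross examination with the presence of tumor tissue at the resection margin". On who decides, "R0/R1 are classified by the pathologist and R2 is classified by the surgeon". The endpoint built on these categories is "Resectability rate (R0R1) and unresectability rate (including R2) among patients with liver-only metastases". The synopsis defines the three categories in the same way, and section 2.1.2 lists the same R0/R1 versus R2 split as a secondary objective.

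Section 6.4 allows treatment to be paused for surgery or for regional procedures (radiofrequency, cryoablation, radiation therapy) if the disease becomes accessible to them. It does not say how a regional procedure enters the resection endpoint.

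**The concern.** The endpoint is a rate over patients, but the categories describe a specimen. The two agree when one operation removes all the disease. They come apart when an operation removes some metastases cleanly and leaves others in the liver, for example the first of two planned operations when the second never takes place. There is then no tumour at the margin, yet the patient still has gross liver disease.

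Patients enter this trial with metastases that cannot be resected with curative aim (section 4.2), and section 1 presents secondary resection as the route to better survival. A reader will therefore take the R0R1 rate as the share of liver-only patients whose liver disease was cleared, and the written definition does not measure that. The trial is uncontrolled, so no second arm carries the same misclassification for comparison.

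**Working it through.** The plan states no expected resection rate, no number of liver-only patients and no power for this endpoint, so there is no figure to reproduce. The check applies the written rule to cases and then sizes one misclassified patient.

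**Step 1: apply the definitions literally.**

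| Patient | At the margin | Score as written | All liver metastases cleared? |
|---|---|---|---|
| All metastases resected, margins clear | No tumour | R0, resectable | Yes |
| Some resected with clear margins, gross metastases left elsewhere in the liver | No tumour | R0, resectable | No |
| First operation R1, second R0 | Two results | R1 and R0; resectable either way | Yes, if nothing remains |
| First operation R2, second R0 clearance | Two results | R2 and R0; rule silent | Yes, if nothing remains |
| Cleared by ablation alone | No margin exists | None; cannot be R0 or R1 | Yes |

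The second row is a wrong result from a stated rule: the R0 condition is met, and the R1 and R2 conditions are not. The third row leaves the combined rate unchanged and blurs only the R0/R1 split. The fourth and fifth rows can lose a cleared patient from the numerator.

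**Step 2: look for a rule elsewhere that would correct this.** Section 2.1.2 repeats the split without a residual-disease condition. Sections 9.4, 10.2 and 10.3 (assessment criteria, populations, methods) say nothing about this endpoint. No section requires all known liver metastases to be removed or ablated before R0 or R1 is assigned, or says which operation counts when there is more than one.

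**Step 3: size.** Let n be the number of liver-only patients, a the number of partial clearances scored R0/R1, and b the number cleared by ablation alone who stay in the denominator without being counted as resectable. Leaving aside the unresolved R2-then-R0 case, the error of the reported rate, read as a rate of complete liver clearance, is

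error = (a − b) / n

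so one patient moves it by 1/n, up or down. Secondary endpoints apply to phase II, planned at 69 patients. The liver-only fraction is not in the documents, so a range is assumed:

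| Assumed fraction of 69 | n | 1/n |
|---|---|---|
| 20% | 13.8, about 14 | 7.1 points |
| 30% | 20.7, about 21 | 4.8 points |
| 40% | 27.6, about 28 | 3.6 points |
| 50% | 34.5, about 35 | 2.9 points |

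Nothing in the documents gives a or b. Either could be zero.

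**The case against.** Three arguments soften the point.

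First, the text may allow a residual-disease reading. R2 is assigned by the surgeon, who sees what is left behind. The unresectability rate is said to include R2, so it holds other patients too. Section 6.4 also uses unresectable as a description of the patient after 12 cycles. This has some weight as evidence of intent, but the definition that follows still confines R2 to the margin, and nothing takes a clear-margin patient out of R0. If some surgeons apply the wider meaning and others the written one, centres will score the same patient differently.

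Second, a reader might infer that the rule can only inflate the rate. The documents do not support that: ablation-only clearance has no margin and falls out of the numerator, and an R2 operation followed by an R0 clearance could be counted either way. This objection stands in full.

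Third, a reader might cite the background sentence "The primary goal for patients who present with technically resectable liver metastases is definitely cure, with R0 resection as the primary goal" as proof that the endpoint was meant to measure cure. That sentence concerns patients who are resectable at presentation, whom this trial does not enrol. The sentences after it on secondary resection are relevant, but they give only general support, and no section calls the resectability rate a measure of curative conversion.

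It is also fair to say that this is one of many secondary endpoints, with no hypothesis or threshold, and that section 10.3 foresees an analysis plan written before the database is closed, where a scoring rule could be settled.

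**Conclusion.** The definition is wrong for a patient-level rate and should be corrected. As written, a liver-only patient with clear margins and gross liver metastases left elsewhere is R0 and resectable, which overstates complete clearance. A patient cleared by ablation alone has no possible R0 or R1 score, which understates it. The net direction is therefore open.

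Each affected patient moves the rate by roughly 3 to 7 percentage points. That rests on an assumed 20 to 50% liver-only fraction of 69 patients, and the number of affected patients cannot be known from the documents.

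The consequence is confined to a secondary endpoint. The 48-week disease-control rate, the rule of at least 29 successes in 65 evaluable patients, and the sample size do not depend on R status.

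**What to change.** Amend the resection definition in section 2.2.2 and the synopsis, and carry it into the analysis plan:

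- Score R status once per patient, after the last planned liver procedure.
- Count R0/R1 only if all known liver metastases were resected, or resected plus ablated, and the worst final margin is R0 or R1.
- Classify as R2, and so unresectable, if gross liver metastasis remains at the margin or elsewhere in the liver.
- Report clearance by ablation alone as a separate, stated category beside the R0R1 rate.

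Two limits keep the rule from creating new errors. It should refer to liver metastases only: synchronous disease is eligible, and a rule about tumour remaining anywhere would turn a primary still in place into R2. Residual disease should be taken from the operation report, not from the next eight-weekly scan, because an early recurrence on that scan could turn a true R0 into R2.

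The cost is the amended wording and one eCRF item (gross liver metastasis remaining after the last planned liver procedure, yes or no). The reported rate may be slightly lower. This is a scoring rule and changes no treatment.
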